In a study comparing the safety and immunogenicity of BNT162b2 vaccine in adolescents to that in adults local and systemic events were generally mild to moderate in severity and were reported at similar frequencies in both age cohorts. As with adults, systemic events were reported more often after BNT162b2 dose 2 than after dose 1. The vaccine produced a greater immune response in adolescents than adults and was highly effective²⁷.

A study assessing two 10 µg doses of BNT162b2 in children 5 to 11 years of age each administered 3 weeks apart, showed the vaccine to be safe, immunogenic and efficacious in this age group as well. Solicited injection site and systemic reactions were generally mild to moderate and lasted 1 to 2 days. In general, systemic events were reported more commonly after the second dose than the first dose. Fever occurred in 8.3% of recipients after the first and second dose.²⁸

Hypersensitivity Reactions and mRNA COVID-19 Vaccines

In the Pfizer mRNA phase III trial, more participants reporting hypersensitivity-related adverse events in the vaccine group (137 [0.63%]) compared with the placebo group (111 [0.51%]). There were no anaphylactic or severe hypersensitivity reactions reported (FDA EUA).

In the Moderna mRNA COVID vaccine phase III trial, more participants reported hypersensitivity-related adverse events in the vaccine group 1.5% of vaccine recipients (258 events in 233 participants) compared with the placebo group 1.1% of placebo recipients (185 events in 166 participants). There were no anaphylactic or severe hypersensitivity reactions with close temporal relation to the vaccine. There was one anaphylactic reaction occurring 63 days after the second dose of the vaccine that did not meet the Brighton Collaboration Anaphylaxis Case Definition (FDA EUA).

There have been numerous reports of anaphylactic reactions after the Pfizer and Moderna vaccine after the start of vaccination campaigns (MMWR January 22, 2021, Vol. 70; MMWR January 15, 2021, Vol. 70). The update on anaphylaxis reports to VAERS following mRNA COVID Vaccines through January 18, 2021 (January ACIP meeting), showed following results:

Table 4. Anaphylaxis reports to VAERS following COVID-19 vaccines.

Characteristic	Pfizer-BioNTech (N = 50)	Moderna (N = 21)
Median age, years (range)	38.5 (26-63)	39 (24-63)
Female (%)	47 (94)	21 (100)
Minutes to symptom onset, median	10	10

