1. Note that Visit 3 is timed relative to Visit 1 but may be conducted on the same day as Visit 3a if Visit 3a occurs 24-28 days after Visit 1. Visit 3 and Visit 4 should not occur on the same day.
2. Note that Visit 4 is timed relative to Visit 2 and may be conducted on the same day as Visit 3a if Visit 3a occurs 24-28 days after Visit 2. Visit 3 and Visit 4 should not occur on the same day.
3. Symptom diary (solicited local and systemic reactogenicity events) to be completed by participant on Days 1-7 after vaccination.
4. Participants completing paper diary only will be called 2-4 days following Visits 1, 2, and 3 as a reminder and to prompt to bring paper diary to next visit
5. Electronic diary records will be reviewed by study staff at days 2-4 days and 8-10 days following Visit 1, 2 and 3.
6. If Visit 3a is conducted by telephone as standard of care these procedures do not need to be performed
7. HRQOL will only be collected for participants 12 years of age and older.
8. Receipt of BNT162b2 within 8 hours of enrollment is permitted
9. Receipt of BNT162b2 within 36 hours prior to study visit is permitted
10. Extended interval beyond 25 days not recommended for persons < 12 years of age

	Table 6: mRNA-1273 (Moderna) Schedule of Events										
Procedure	Visit 1	Visit 1a	Visit 2	Visit 2a	Visit 3 ¹	Visit 3a	Visit 3b	Visit 4 ²	Visit 5	Visit 6	Un-Scheduled
	Clinic	Phone/Text /Email/Data Review ^{3,4,5}	Clinic	Phone/Text /Email/Data Review ^{3,4,5}	Clinic	Phone/ Clinic	Phone/Text /Email/Data Review ^{3,4,5}	Clinic	Clinic	Phone	Clinic
Estimated Study Day (Relative to Visit 1)	1	1-7	8-15	8-15(+6)	29	29-57	29-57(+6)	36-43	57-85	121	
Time Following Visit 1 (Days) [Window]	0	0-6	7-14 [+2]		28 [+/-4]	28-56 [+/-4]				120 (+/-14)	
Time Following Visit 2 (Days) [Window]				0-6				28 [+/-4]			
Time Following Visit 3a (Days) [Window]							0-6		28 [+/-4]		
Informed consent & Medical Release of Information	X										
Review Eligibility Criteria	X										
Review Temporary Delay Criteria	X		X			X ⁶					
Demographic and Health History	X										
Influenza and COVID-19 Vaccination History	X										
Obtain unsolicited adverse events			X		X	X		X			
Obtain SAE and AESI information			X		X	X		X	X	X	X
Concomitant medications	X		X		X	X		X	X	X	X
Additional COVID-19 vaccinations										X	
HRQOL measure ⁷	X	X									
Measure temperature	X		X			X ⁶					X
Venipuncture	X				X ⁴			X ⁴	X		
Randomization	X										
Vaccination with COVID-19 vaccine	X ⁸					X ^{9,10}					

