- Participant will either receive or have just received (within 36 hours) mRNA COVID-19 vaccine per local standard of care or mRNA COVID-19 vaccine will be administered in the deltoid muscle by trained, licensed research staff as described in Section 5.3.1.
- Ensure participants/participant's LAR(s) receive the respective fact sheet for mRNA COVID-19 vaccine during visit.
- Dispense paper memory aid, thermometer if needed, and ruler if needed (in order to standardize measurements). Review instructions for use of thermometer, ruler, and electronic memory aid completion.
- Observe participant for a minimum of 30 minutes (if mRNA COVID-19 vaccine is given at the study visit) and assess for any immediate reactogenicity symptoms
- Confirm date of next appointment

Visit 3b, Study Days 1 – 7 Post Visit 3

- Participants/participant's LAR(s) complete electronic or paper solicited symptom diary each day at approximately the same time each day for days 1-7
- Participants/participant's LAR(s) using paper diary:
 - Study staff will call participants/participant's LAR(s) on days 2-4 following Visit 3 as a reminder to fill out the symptom diary on day 1-7 post Visit 3 regarding reactogenicity events and to bring the diary card to the next visit
 - Participants/participant's LAR(s) will be:
 - Asked to notify the study staff if they or their child is hospitalized or have a severe adverse event
 - Follow up with their or their child's healthcare provider if they have symptoms they find concerning
- Participants/participant's LAR(s) using REDCap web-based system:
 - Study staff will send reminders to fill out the symptom diary on day 1-7 post Visit 3 regarding reactogenicity events.
 - Study staff will review REDCap system to confirm data capture and assess for any AE or SAEs on 2-4 days and 8-10 days following Visit 3
 - The study team will contact participants/participant's LAR(s) if they have any missing information. The study team may also contact participants/participant's LAR(s) if more information is needed to better describe AEs [including SAEs and severe (Grade 3) events] reported in the REDCap web-based system.
 - All participants/participant's LAR(s) using the REDCAP web-based system will be:
 - Asked to notify the study staff if they or their child is hospitalized or have a severe adverse event
 - Follow up with their or their child's healthcare provider if they have symptoms they find concerning

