At the time of study enrollment, participants/participant's LAR(s) will be given a thermometer and instructed on using the symptom diary to document oral temperatures and post-injection symptoms. Beginning on the evening of Study Visits 1, 2 and 3 (if primary two-dose COVID-19 vaccine series) (Day 1) following vaccination, participants/participant's LAR(s) will record their or their child's oral temperature using the study-supplied thermometer, the occurrence of solicited AEs, for the next 7 days (Day 1 – 7). Temperature will be recorded at roughly the same time each day. If a temperature $\geq 100.0^{\circ}\text{F}$ (37.8°C) is recorded, a second measurement will be taken. If more than one temperature is taken on the same day, the highest temperature should be recorded. Fever will be defined as a measured temperature $\geq 100.4^{\circ}\text{F}$ (38.0°C). Participants/participant's LAR(s) will be queried during Visits 2, 3, and 4 on any solicited adverse events following vaccination. Injection site reactogenicity will be assessed separately for COVID-19 vaccine and IIV4 or placebo as described in **Table 8**.

Table 8. Injection-site Reactogenicity Grading

Local Reaction to Injectable Product	Mild (Grade 1)	Moderate (Grade 2)	Severe (Grade 3)	Potentially Life Threatening (Grade 4)
Pain	Noticeable but does not interfere with activity	Interferes with activity but did not need a medical visit or absenteeism [i.e. missing work or school]	Significant; prevents daily activity and/or resulted in medical visit and/or absenteeism [i.e. missing work or school]	Requires an emergency room (ER) visit or hospitalization
Induration/Swelling (≥ 12 years of age)	2.5 – 5 cm	5.1 – 10 cm	> 10 cm	Requires an emergency room (ER) visit or hospitalization
Induration/Swelling (< 12 years of age)	0.5 – 2 cm	2.0 -7.0 cm	> 7 cm	Requires an emergency room (ER) visit or hospitalization
Erythema/Redness (≥ 12 years of age)	2.5 – 5 cm	5.1 – 10 cm	> 10 cm	Requires an emergency room (ER) visit or hospitalization
Erythema/Redness (< 12 years of age)	0.5 – 2 cm	2.0 -7.0 cm	> 7 cm	Requires an emergency room (ER) visit or hospitalization

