#### 3.2 Secondary

- a) SOM1a: Comparison of the proportion of participants reporting at least one solicited reactogenicity event to include fever, chills, myalgia, or arthralgia of moderate or greater severity in the Simultaneous group with the Sequential group within 1-7 days following Vaccination Visit 1 visit during which participants receive either IIV4 or placebo with an mRNA COVID-19 vaccine.
- b) SOM2a: Comparison of the proportion of participants reporting at least one solicited reactogenicity event to include fever, chills, myalgia, or arthralgia of moderate or greater severity in the Simultaneous group with the Sequential group within 1-7 days following Vaccination Visit 2 during which participants receive either IIV4 or placebo without an mRNA COVID-19 vaccine.
- c) SOM3a: The proportion of participants in each vaccination group reporting specified solicited local and systemic reactogenicity events of any severity and by severity grade within 1-7 days following the first vaccination visit during which participants receive either IIV4 or placebo with an mRNA COVID-19 vaccine.

SOM3b: The proportion of participants in each vaccination group reporting specified solicited local and systemic reactogenicity events of any severity and by severity grade within 1-7 days following the second vaccination visit during which participants receive either IIV4 or placebo.

SOM3c: The proportion of participants in each vaccination group reporting specified solicited local and systemic reactogenicity events of any severity and by severity grade within 1-7 days following the third vaccination visit during which all participants receive an mRNA COVID-19 vaccine alone for those receiving two doses of mRNA COVID-19 vaccine.

- d) SOM4a: The proportion of participants in Simultaneous and Sequential Groups with at least one serious adverse event occurring during the study period and a description of each event.

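### When dose 2 is given before Visit 3a (up to 36 hours is allowed), no diary runs until the visit, so short reactions may be under-counted in the dose-2 outcomes

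*Protocol*

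**What the plan says.** **When dose 2 may be given.** Protocol Section 5.1.1, Visit 3a, allows the dose to precede the visit: "Participant will either receive or have just received (within 36 hours) mRNA COVID-19 vaccine per local standard of care". Table 5 footnote 9 agrees: "Receipt of BNT162b2 within 36 hours prior to study visit is permitted". Table 6 carries the same footnote. Visit 3a may be a telephone contact. Study staff may also give the dose at the visit itself.

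**When the diary starts.** The Visit 3a procedures include: "Dispense paper memory aid, thermometer if needed, and ruler if needed (in order to standardize measurements". Tables 5 and 6 also place the handover of the diary link at Visit 3a and run Visit 3b from 0 to 6 days after it. Section 5.4 starts recording "Beginning on the evening of Study Visits 1, 2 and 3 (if primary two-dose COVID-19 vaccine series) (Day 1) following vaccination".

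**A second clock.** Table 5 footnote 3 reads: "Symptom diary (solicited local and systemic reactogenicity events) to be completed by participant on Days 1-7 after vaccination". Section 5.4 also refers to follow-up through post-vaccination Day 7.

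**What the endpoint assumes.** SAP Section 3.2, SOM3c, counts 1 to 7 days "following the third vaccination visit during which all participants receive an mRNA COVID-19 vaccine alone for those receiving two doses". EOM1a and EOM2c in SAP Section 3.3 are built the same way.

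**The concern.** When the injection and Visit 3a fall on the same day, the two clocks agree. When the injection comes first, they do not, and no rule says which one governs or how earlier symptoms are entered. Under the visit-based rules, a participant vaccinated the day before has seven entries covering days 2 to 8 after the injection, and the evening of the injection has none.

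The protocol's tables show systemic reactions to be commoner after dose 2 than after dose 1. For BNT162b2 at 16-55 years, chills rise from 14.0% to 35.1%. For mRNA-1273 in the younger adult group, fever rises from 0.9% to 17.4%. For children aged 5 to 11, Section 1.1 says: "Solicited injection site and systemic reactions were generally mild to moderate and lasted 1 to 2 days". A short reaction could therefore end, or fall to a lower grade, before the first entry. At stake are the dose-2 proportions in SOM3c, EO1/EOM1a and EOM2c and, less directly, EOM2d and the 3c parts of EOM5a and EOM6a. SAP Section 9 plans a sensitivity analysis only for switched study product, so no planned analysis would reveal the under-count.

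**Working it through.** **Plan's own figure.** The plan states no figure on this point. Its one design figure, 82.6% power, reproduces: Φ(0.10/√(2×0.15×0.85/214) − 1.96) = Φ(2.897 − 1.960) = 0.826. It concerns the primary endpoint and is not used below.

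**Step 1: the clocks side by side**

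| Source | Day 1 counted from |
|---|---|
| Protocol Tables 5 and 6, Visit 3b | Visit 3a |
| Protocol 5.4, start of recording | evening of the visit |
| Protocol Table 5 footnote 3 | vaccination |
| SAP SOM3c, EOM1a, EOM2c | the visit, with the vaccine assumed given there |

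The visit label is also unclear. Section 5.4 says Visit 3, but in Tables 5 and 6 Visit 3 is the Day 29 blood draw and the injection belongs to Visit 3a.

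**Step 2: entries missed.** Assume an evening entry at 20:00 and a visit between 08:00 and 17:00.

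- Dose the same day between 08:00 and 17:00: lag 0 to 9 h, 0 entries missed.
- Dose the previous day between 08:00 and 17:00: lag 15 to 33 h, 1 entry missed.
- Dose two days earlier between 08:00 and 17:00: the shortest lag is 39 h (17:00 to 08:00), beyond the 36 h allowed.
- Two entries are missed only at the limit: dose at 20:00, visit at 08:00 two days later, lag 36 h.

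**Step 3: do the planned backups reach these symptoms?**

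- Section 5.4 queries solicited events at Visits 2, 3 and 4, nominally Days 8-15, 29 and 36-43. Dose 2 may come as late as Day 57. With the stated windows, the latest Visit 2 is 14 + 2 = 16 days after Visit 1 and the latest Visit 4 is 16 + 28 + 4 = 48 days after Visit 1, which is Day 49. A dose after that has no later query, because Visit 5 records only serious events and events of special interest.
- Contact about missing information is listed for electronic diary users. Paper users get a reminder call. Under a visit-based clock, days before the diary opens are not missing entries.
- Fever requires a measured temperature, and redness and swelling are graded in centimetres. If they were not measured at the time, recall does not supply them.

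**Step 4: size.** Let p be the true proportion with the event, s the share of two-dose participants vaccinated before the visit, and m the share of their events over before the diary starts and not recovered. Then recorded rate = p(1 − s·m). The documents give neither s nor m, so the values below are assumptions. Each cell is the fraction of the true rate that is kept, 1 − s·m.

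| s | m = 0.25 | m = 0.50 | m = 1 |
|---|---|---|---|
| 0.10 | 0.975 | 0.95 | 0.90 |
| 0.25 | 0.938 | 0.875 | 0.75 |
| 0.50 | 0.875 | 0.75 | 0.50 |

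For two arms, the recorded difference is p₁(1 − s₁m₁) − p₂(1 − s₂m₂). It reduces to (p₁ − p₂)(1 − s·m) only if s and m are equal in both arms.

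The factor does not carry over to EOM2d. A participant with a qualifying event after Visit 1 or 2 is already counted there, so only those whose sole event followed dose 2 can be missed.

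**The case against.** The strongest reply is that this is a wording gap with limited reach.

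- **Few may be affected.** Only two-dose participants vaccinated before Visit 3a are involved. Section 1.2 expects most adults and many children to receive a booster, and study staff may give dose 2 at the visit. This stands, and it is why s cannot be assumed large.
- **The shortfall is small.** A reader might infer that two of the seven reaction days are missed. Step 2 shows that two entries is the limiting case and that zero or one is usual.
- **The reaction peak is not shown to be missed.** A reader might infer that the diary skips the time when reactions occur. The documents give a duration for children aged 5 to 11 only, and no onset day for mRNA vaccine reactions at any age. A reaction still present on the first diary evening is recorded.
- **Some symptoms will be recovered.** Sites that follow the footnote would count from vaccination. If Visit 3 or 4 coincides with Visit 3a, the query comes within 36 hours of the dose. For children under 12, Table 5 footnote 10 advises against intervals beyond 25 days, so dose 2 nominally falls on Days 22-26 and the Day 29 query follows 3 to 7 days later. This is a real safeguard, but it relies on recall and fails for late doses and for measured signs.
- **No confirmatory result depends on it.** SOM3c is descriptive. EO1 is an exploratory two-sided comparison, so dilution cannot produce a false noninferiority finding. The allowance applies alike to both arms under observer blinding, and both receive mRNA vaccine alone at that visit.

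What survives is the conflict itself: followed as written, the visit-based rules leave a gap that the backups do not fully close.

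**Conclusion.** The concern holds for two-dose participants vaccinated before Visit 3a. Their symptoms before the visit are not prospectively recorded, usually a loss of zero or one evening entry and at most two. Short reactions may be under-counted in SOM3c, EO1/EOM1a and EOM2c, and to a lesser degree in EOM2d and the 3c parts of EOM5a and EOM6a.

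The size is unknown. If s·m lies between 0.025 and 0.5, 97.5% to 50% of the true rate is kept. That range is assumed, and the lower end needs half of the participants vaccinated early with none of their events persisting or recovered. A between-arm difference shrinks by the same factor only if s and m are equal across arms, which blinding makes plausible but does not guarantee.

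The documents do not support reading this as a general loss of dose-2 data or as a threat to the main result. The primary endpoint, SO1 and SO2 use Visits 1 and 2 and are unaffected.

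**What to change.** 1. Reconcile Protocol Tables 5 and 6, the Visit 3a and 3b text, Section 5.4, and SAP Sections 3.2 and 3.3 so that dose-2 diary Day 1 is the calendar day of the injection. Use the label Visit 3a wherever the dose-2 visit is meant.
2. Give primary-series participants the dose-2 diary or link before the earliest dose-2 date, for example at Visit 2 and labelled separately from the Visit 2 diary. The participant starts it on the day of injection.
3. Record the date and time of dose 2.
4. Where the diary still starts late, enter the elapsed days at Visit 3a and flag them as recalled.
5. Repeat SOM3c and EO1 without the participants whose diary started late. If collection has finished, this can still be done where the injection date and time are available.

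The cost is protocol and SAP wording, a change to the diary set-up and one extra table. The drawbacks are some recalled days, a diary held for several weeks before use, and reliance on participants to start it. Nothing changes in who gives the vaccine or when.

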5.2 Treatment Assignment Procedures

This study is a prospective, randomized, observer-blinded, clinical trial involving subjects aged \geq 5 years of age who are to receive COVID-19 and IIV4 vaccines.

5.2.1 Randomization

Participants will be randomized (1:1) to receive either IIV4 or saline by an unblinded vaccinator at Visit 1. Those receiving IIV4 at visit 1 will receive saline placebo at Visit 2 and those receiving saline placebo at Visit 1 will receive IIV4 at Visit 2. Randomization will be stratified by age (5 to $<$ 12 years of age, 12 to $<$ 18 years of age, 18 to $<$ 65 years of age, and \geq 65 years of age) and receipt of either a primary two-dose series or any booster dose of mRNA COVID-19 vaccine (for ages booster is authorized and recommended) using a permuted block randomization scheme stratified by Lead and Contributing Sites. The project statistician will generate permuted block randomization schemes which will be uploaded to REDCap. The randomization schedule will not be available to the study staff, so the next randomization allocation will not be known before randomization occurs. Following confirmation of study eligibility criteria during Visit 1, participant randomization will be through REDCap with treatment allocation recorded on the unblinded vaccinator CRF. In the event that REDCap is unavailable, manual randomization will occur through the use of envelopes. The project statistician will prepare 10 envelopes per age group and vaccine series per site (total of 60 per site) that will use the same randomization strategy as the primary scheme embedded in REDCap. When an unblinded team member is informed of the age group, he/she will pull the next envelope in order. In order to capture the allocation per subject, a separate form in REDCap will be used by the unblinded personnel to add the assignment. A log will need to be kept at the site capturing these instances.

5.3 Data Collection**5.3.1 Study Product Supply, Storage, and Administration**

In order to ensure adherence to study randomization assignment, age-appropriate, licensed IIV4 or saline placebo will be administered as a study procedure. EUA or approved mRNA COVID-19 vaccine will be administered either per standard of care or as a study procedure depending

on the study site and location. Licensed SD-IIV4 and HD-IIV4 vaccine (prefilled syringes) will be purchased for study administration and maintained at the study sites and stored at 2°C to 8°C in a research-specific medication refrigerator. Licensed or EUA COVID-19 vaccine will be stored per manufacturer specifications. While research staff maintain daily temperature logs for the medication storage, it is also monitored 24/7 with alarm activation if out of range. Research staff are notified of any alarm activations and have an on-call system in place to report to the research center for further investigation. Any potentially compromised vaccine will be quarantined for further disposition based on site-specific SOPs and investigator assessment.

A licensed unadjuvanted standard dose egg-based IIV4 will be the designated study product for influenza vaccination of persons less than 65 years of age⁴⁴. Study sites will work to coordinate the brand of IIV4 administered. A single administration of IIV4 comprises intramuscular delivery of 0.5mL total volume of the vaccine for persons 5 through 64 years of age.

Fluzone High-Dose (Sanofi) will be the designated study products for influenza vaccination of persons 65 years of age and older. A single administration of HD-IIV4 comprises intramuscular delivery of 0.7mL total volume of the vaccine for adults 65 years of age and older.

Sterile normal saline supplied by each site's respective pharmacy will be used as placebo. A single administration of placebo comprises intramuscular deliver of 0.5 mL total volume of normal saline for persons 5 through 64 years of age and 0.7 mL total volume for those 65 years of age and older.

mRNA COVID-19 vaccine will be administered per FDA and ACIP recommendations for administration. The primary two-doses mRNA COVID-19 vaccine series will be administered in two doses, approximately 21 to 56 days or 28 to 56 days apart depending upon the FDA or CDC recommendations. The booster dose of mRNA COVID-19 vaccine will be administered according to FDA authorization or EUA and ACIP recommendation.

Vaccine lot numbers, dose, and site of vaccine administration will be recorded by research staff. After administration, used study syringes will be disposed of according to standard operating procedure.

Emergency management supplies including epinephrine (1:1000) and trained staff will be available for initial treatment of an allergic reaction, if needed.

